4.6.2.2 Data Safety Monitoring

A DSMB is not required because multiple clinical sites will not be used, the study is not blinded, and interventions are not particularly high risk or vulnerable populations are not included.

Data and safety monitoring plan:

[name] will be monitoring adverse events involving data loss and adverse events related to the study. Adverse events will be monitored in the following ways:

- 1) Many elements of the research plan are intended to minimize the risks of study participation. Co-investigators will be available to subjects in the event of an emergency. In the event that serious medical or mental health complications should occur, consultation from emergency clinical services is immediately available at the Bedford VA Hospital.
- 2) Weekly meetings will be held between Drs. [name] and [name]. We will discuss and resolve any safety issues more frequently if necessary, as such issues arise, possible participant withdrawal from the study, or any safety concern.
- 3) Drs. [name] and [name] will observe and ensure that data are locked in designated file cabinets and data stored electronically are password-protected and not moved outside the VA. Data integrity and confidentiality will be safeguarded as discussed in the Data Management section of the application and under Protection Against Risks above.
- 4) Data integrity and confidentiality will be safeguarded as discussed in the Data Management section of the application and under Protection Against Risks above. We will report data security incidents to the IRB, privacy, and information security (e.g., theft or loss of data or storage media, unauthorized access of sensitive data or storage devices or non-compliance with security controls) as soon as we learn of these incidents.

Reporting Adverse Events: Reporting of adverse events will occur as follows:

Local Research Deaths. The IRB will be notified immediately upon becoming aware of any local research death that is both unanticipated and related to the research. A written notification to the IRB will be submitted within

5 business days of becoming aware of the death. If the death does not appear to be both unanticipated and related to the research, it will be recorded and reported at continuing review.

Local SAEs. The IRB will be notified in writing within 5 business days after becoming aware of any local Serious Adverse Event or Serious Problem that is both unanticipated and related to the research. If the serious adverse event or serious problem does not appear to be both unanticipated and related to the research, it will be recorded and reported at continuing review. We will reach out to the local research office if we have any questions.

Serious Problems Involving Information Security. The ACOS/R&D, Information Security Officer (ISO), Privacy Officer (PO), and relevant investigators will be notified immediately (i.e., within one hour) upon becoming aware of information security incidents related to VA research that appear to represent a serious research information security problem, including any inappropriate access, loss, or theft of PHI; noncompliant storage, transmission, removal, or destruction of PHI; or theft, loss, or noncompliant destruction of equipment containing PHI. The ACOS/R&D will be notified in writing 5 business days of becoming aware of any of these incidents.

Apparent Serious or Continuing Noncompliance. The IRB will be notified, in writing, within 5 business days after becoming aware of any apparent serious or continuing noncompliance with IRB or other human research protection requirements.

4.6.3 Potential Benefits:

There is no direct benefit to the clinical-care providers or Veterans participating in this study. However, participating may benefit by exploring a new and emerging technology, and providing their input on potential future directions for its usage. Moreover, this research will help to understand better what potential areas for pain self-management interventions may best be suited to this platform or at-home care from the perspective of clinical care providers. The feedback gained from this study will provide direction for refinement of the VACT-CP system, as well as inform methods for a future research studies on the utilization and programming of VACT-CP. Because these anticipated benefits are very important to the field, the fairly minimal risks that the study poses are reasonable. Therefore, to improve knowledge about the potential effectiveness and usability of the VACT-CP system, it is important that these aims of this study be addressed and that providers – key referral sources, content experts, and stakeholders - have the opportunity to provide feedback on the technology. This study has the potential to not only improve the treatment of Veterans with chronic pain, but also advance the field of at-home tech supported mobile interventions by further exploring usability and interest of Veterans in this platform for chronic pain management. In addition, this suggests that the VA could benefit from the rapidly increasing field of online and mobile health technology for increased access to empirically supported chronic pain treatment. Web-based interventions in particular have been growing in popularity as a treatment-delivery method for many psychiatric and behavioral difficulties. Online interventions have the potential to reach Veterans who might otherwise not have access to VA clinical care, as 85% of adults have access to either the Internet at home or wireless mobile devices.

Online health and clinical treatments are increasingly appealing to potential consumers and appeal to health centers because telehealth delivery methods can improve their ability to reach patients, are cost-effective, and can increase overall impact. Following the initial program development, web-based behavioral interventions are relatively easy to implement within clinical and health settings compared to in-person individual or group interventions, since they do not require training new

practitioners to implement a treatment model or monitor treatment fidelity. Once developed, a self-guided, web-based ACT intervention for Veterans with chronic pain would provide primary care physicians and clinicians with a new referral option--one that requires no knowledge of ACT.

4.6.4 Alternative Procedures.

There are no alternative procedures available, as this is not a treatment study. Participants are free to decline entrance into or withdraw their participation in this study at any time. However, if Veterans decline to participate or withdraw from the study, and they indicate that they desire pain management treatment, they will be provided with information about treatments in the VA. Chronic pain treatments at the VA include individual and group counseling, telephone counseling, complementary and alternative interventions (e.g., acupuncture), and pharmacological options. A decision not to participate in this study or to withdraw from this study will not affect the participant's ability to participate in standard VA treatment.

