Week 2	Behavioral Change and Triggers	Veterans will also register and make distinctions between primary and secondary pain (to distinguish physiological and psychological consequences of pain, as well as being introduced to the behavioral model and concepts of behavioral change when experiencing cognitive barriers to change. Internal (e.g., thoughts, feelings, bodily sensations) vs. physiological pain triggers and concerns will be identified, and their role as a perceived obstruction for living a meaningful life will be discussed.
Week 3	Values Clarification	The Veteran will be introduced to goal setting and committed action, which will be explicitly linked to both values and functional goals, as well as invited to explore additional activities for pain management included on the site (e.g., stretching, yoga, progressive muscle relaxation). Veterans will clarify their values and goals for treatment, using a personalized values-assessment.
Week 4	Acceptance	Veterans will be encouraged to face pain-related experiences with mindful acceptance. Veterans will engage in acceptance exercises (e.g., willingness to experience painful sensations, rather than avoid them) that are linked to previously identified values. Veterans will also participate in mindfulness exercises in order to practice nonjudgmental acceptance of internal pain-related experiences.
Week 5	Cognitive Defusion	Veterans will be introduced to be pacing vs. activity cycling while getting psychoeducation on the nature of language and cognitive barriers to committed action. The Veteran will be helped to learn that they are not their thoughts related to pain, anxieties, or fears, and practice mindfully observing and accepting these internal experiences, rather than try to avoid them.
Week 6	Committed Action (Behavioral Activation)	This module will provide metaphors and discuss willingness to experience discomfort as a means to pursue important outcomes. Veterans will be asked to incorporate more pleasant events in their lives to replace pain-avoidant behaviors used to fill idle time. Veterans will also be asked to identify a behavioral, functional goal over the next week that will potentially cause them some discomfort, but is aligned with a valued life area.

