Phase Three: Following recruitment, a research associate not otherwise involved in the study will screen participants prior to enrollment. Veterans will be randomized in a 1:1 ratio, with a research staff member utilizing and keeping the schedule. Veterans randomized to VACT-CP (and online website that includes 7 online-module based weekly sessions of treatment) via personal computer or provided laptop at the Bedford VAMC. Veterans in the waitlist control will be provided with a list of common pain resources at the Bedford VAMC. The VACT-CP program will be housed on a secure web server through Northeastern University, with no Veteran private health information collected by the system. Veterans in both conditions will complete the assessment battery (see Table 2 for specific schedule) at baseline, either in-person or remotely (via a phone call or online using the VA-approved Qualtrics survey platform) depending on the participant’s preference. In addition, the full battery of primary outcomes and process measures will be taken at mid-point of the intervention phase (3 weeks) and at the end, immediately following the treatment (7 weeks). Veterans will be tracked in terms of their post-referral treatment engagement (e.g., enrolling in any of the pain-resource options on the handout). In addition, a research associate will call the Veteran at weeks 3 and 6 and conduct a brief safety assessment with Veterans assess for potential suicidality, usability issues, and participant health and well-being.

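### Phase 3 monitors non-serious adverse events only if study-related, so they are likely to be under-recorded in the wait-list arm and cannot be compared reliably between arms

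*Combined protocol and SAP*

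**What the plan says.** Section 4.6.2.2 sets the scope of routine monitoring: a designated team member "will be monitoring adverse events involving data loss and adverse events related to the study". It also gives, among its reasons for having no DSMB, that "the study is not blinded".

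For the gravest events the section separates recording from relatedness. For deaths: "If the death does not appear to be both unanticipated and related to the research, it will be recorded and reported at continuing review". For serious adverse events, one that "does not appear to be both unanticipated and related to the research, it will be recorded and reported at continuing review". In both cases relatedness and expectedness set the reporting timeline, not whether the event is recorded. There is no matching provision for non-serious events.

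The plan does schedule contacts at which such events could surface. Section 3.3 (Phase Three) says "a research associate will call the Veteran at weeks 3 and 6 and conduct a brief safety assessment with Veterans", in order to "assess for potential suicidality, usability issues, and participant health and well-being". Section 4.6.1 (Phase Three) makes clear that suicide-risk monitoring, with staff assessments at weeks 3 and 6, covers both conditions.

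The arms differ in what Veterans are asked to do. Table 1 of section 3.3 has VACT-CP Veterans invited to stretching and yoga (Week 3), practising willingness towards painful sensations (Week 4), and asked in Week 6 to "identify a behavioral, functional goal over the next week that will potentially cause them some discomfort". Wait-list Veterans are given a list of common pain resources and may use the program only after the one-month follow-up (section 3.2).

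**The concern.** A scope rule that depends on relatedness is likely to act differently in the two arms. A strained back or a pain flare in a VACT-CP Veteran who has been stretching or pursuing an uncomfortable goal can plausibly be attributed to the study. The same event in a wait-list Veteran has little in the study to be attributed to. In people with chronic pain, the cause of a single flare can rarely be settled case by case. The randomized comparison is the better guide to an excess, and it needs events recorded alike on both sides.

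The error can go either way. VACT-CP may show an excess that comes only from attribution. Or a true excess may vanish because the team regards the flares as ordinary chronic pain. Section 3.5 (Aim 3c) says this phase will inform the design of a larger efficacy trial, so a misleading count of non-serious events could be carried forward.

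**Working it through.** The plan gives no adverse-event figure to reproduce, so the check is mainly a comparison of the text, followed by an illustration whose inputs are assumed.

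**Recording by type of event**

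- Deaths and serious events: recorded regardless of relatedness, both arms (section 4.6.2.2).
- Suicidality: Columbia scale at each assessment session, plus the week 3 and 6 assessments, both arms (section 4.6.1). The scale has no row in Table 2 of section 3.4.
- Depression, health status including bodily pain, and pain-related function: PHQ-9, VR-36 and POQ-SF at all four time points. These rows of Table 2 carry no asterisk, so both arms complete them.
- Non-serious events such as injuries or between-visit flares: in scope of monitoring only if related to the study. There is no adverse-event definition, no standard question and no rule for logging unrelated events.
- Between-visit pain ratings: taken at the start of each module (section 3.4, Pain-related Measures), so during the comparison only VACT-CP Veterans have them. This makes a flare easier to notice in that arm.

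**Illustration (assumption-driven)**

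Inputs from the plan: 20 Veterans per arm (section 3.2) and 30% attrition after randomization (section 3.3). Assumed: the true proportion *r* with at least one non-serious event is equal in both arms, 20% to 60%. The share judged related is *s*: 30% to 50% in VACT-CP, 0% to 10% in wait-list.

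Expected number recorded per arm = 20 × *r* × *s*. Spurious difference = *r* × (*s* in VACT-CP − *s* in wait-list).

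| True rate | Share judged related, VACT-CP / wait-list | Expected recorded, VACT-CP v wait-list | Spurious difference |
|---|---|---|---|
| 20% | 30% / 10% | 1.2 v 0.4 | 0.20 × 0.20 = 4 points |
| 40% | 50% / 5% | 4.0 v 0.4 | 0.40 × 0.45 = 18 points |
| 60% | 50% / 0% | 6.0 v 0 | 0.60 × 0.50 = 30 points |

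The true difference is zero in every row. In the other direction, a true 8 of 20 v 2 of 20 would appear as 0 v 0 if no event were judged related. Equal attrition, to 20 × 0.70 = 14 per arm, would lower the counts but leave the expected difference in points unchanged.

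**What full recording would deliver**

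With no events in an arm, the one-sided 95% upper bound on the true rate is 1 − 0.05^(1/n): 13.9% for n = 20 and 19.3% for n = 14. Power to separate 20% from 40% (two-sided 5%, normal approximation with pooled null variance) is Φ[(0.20 − 1.96 × 0.1449) / 0.1414] = Φ(−0.59), about 28%, at 20 per arm, and about 20% at 14 per arm. Complete recording therefore supports description, not a test.

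**The case against.** The strongest reply is that much of the harm of interest is already captured without the filter, and that point stands. A reader might infer that harm cannot be compared between the arms at all. The documents do not support that, given the unfiltered recording of serious events and the instruments common to both arms. Worsening pain and function at visits is measured by VR-36 and POQ-SF. Those are scores at fixed visits, however, and do not count injuries or flares between them.

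A reader might also infer that wait-list events drop out by construction. That too goes beyond the text. Relatedness is to the study, not to the intervention, and section 4.6.1 names discomfort from assessments and questionnaires and loss of confidentiality as study risks, which can arise in wait-list Veterans. Under-recording of flares and injuries is likely, not certain.

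It can further be said that no sentence orders unrelated non-serious events to be discarded, and that the weekly safety meetings in section 4.6.2.2 may take up any safety concern. This is correct, but discussion at a meeting is not a recording rule, and the only stated scope for non-serious events is the related ones.

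Finally, no aim compares adverse events by arm; Aim 3b in section 3.5 reports means and standard deviations of listed outcomes. So no planned analysis is invalidated. What is at risk is any count of non-serious events later drawn from the safety record.

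**Conclusion.** The concern holds for non-serious adverse events in Phase 3. The stated scope is limited to study-related events, relatedness is judged unblinded, and the arms differ in how readily an event can be attributed to the study. Wait-list events are therefore likely to be under-recorded relative to VACT-CP, and counts of non-serious events are not a reliable basis for comparing arms.

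The size cannot be derived from the documents. The range of 4 to 30 points depends entirely on the assumed event rates and attribution shares, and the direction could reverse if flares in VACT-CP are put down to ordinary chronic pain. Even with full recording, 20 per arm allows description only. The change is still worth making, because the protocol already applies the principle to deaths and serious events and the necessary contacts are already scheduled.

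**What to change.** In section 4.6.2.2, keep the existing sentence for Phases 1 and 2, whose participants are never randomized and would fall outside a rule that starts at randomization. Add for Phase 3:

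*All adverse events in both arms, from randomization to the one-month follow-up, will be recorded whatever the cause, using the same question in both arms at the week 3 and 6 calls and the scheduled assessments; relatedness and expectedness will be recorded as separate fields and used only for the IRB reporting timelines.*

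This window closes before wait-list Veterans are offered the program. In section 3.5, Aim 3b, add a descriptive count by arm of Veterans with at least one adverse event, without significance testing.

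The cost is a sentence in each of two sections and a line on the existing call and assessment forms. The downside is a longer list of minor, mostly unrelated events.

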4.7 Costs and Payments

Phase 1: There will be no payment to providers who are subjects.

Phase 2: Participants will receive \$40 for their research session, which should take approximately two hours. This will be provided in the form of a \$40 CVS gift card that is mailed to participants after their research session.

Phase 3: Subjects will be paid \$60 for the baseline assessment, \$40 at the midpoint testing visit, and, \$60 for the end of treatment (Session 7) and \$40 for a one-month follow-up (total; \$200 CVS gift cards).

4.8 Providing for Reuse of Data

Data will not be reused.

4.9 Creation of a Tissue Bank

We will not be creating a tissue bank.

5.0 Resources

Funding for this study has been secured through an RR&D Career Development Award (PI: [name]), and will provide sufficient staff support for the conduct of this study and protection of human subjects and programming support for any interactive changes made to the VACT-CP system. The PI is research faculty within the Social and Community Reintegration Research Program and MIRECC, which provides space and staff for this study. The SoCRR and MIRECC program involves several researchers from the Bedford VA and VISN 1 that are community reintegration experts. Study activities will take place either remote or in the offices of MIRECC in Building 5. VISN 1 MIRECC has purchased the use of the Qualtrics platform for collecting data.

6.0 Collaborations

We will work with Northeastern University, who will host the VACT-CP website and collect deidentified participant usage data during usability testing.

